For each index admission we will calculate a set of quality and safety indicators, which have been validated for use with administrative data and are widely used for performance assessment in regulatory contexts (for example in monitoring against the NHS Outcome Framework, in CQC inspections/reviews, in clinical governance and appraisal/revalidation processes, etc) and for research purposes:

- 1) Unplanned readmission to hospital within 28 days of discharge (binary: yes/no),
- 2) Unplanned emergency department attendance within 28 days of discharge (binary: yes/no),
- 3) Emergency transfers to NHS hospitals at the end of the index admission episode (binary: ves/no).
- 4) Total length of continuous inpatient stay (accounting for transfers between hospitals) (continuous).
- 5) Death within 30 days of admission (binary: yes/no), and
- 6) Patient-reported health improvements within the first 6 months after surgery (for hip and knee replacement only) (continuous).

Each indicator will be summarised for index admission for quadrants A, B and C. Indicators 1-4 are constructed by linking index admissions to subsequent episodes of hospital care within Hospital Episode Statistics, which allows for such longitudinal follow-up through the use of a unique pseudonymised patient identifier (the Master Person Service ID). For indicator 2, we will additionally link admitted patient data to the Hospital Episode Statistics Emergency Care dataset, which captures all emergency department attendances in English hospitals from 2021.

Indicator 5 is constructed by linking Hospital Episode Statistics data to official Civil Registration data on date of death held by the Office for National Statistics. This linkage is performed by NHS Digital

based on the patient-identifiable data (e.g name, date of birth, NHS number) they hold. We will also consider an alternative outcome indicator based on in-hospital deaths as recorded in Hospital Episode Statistics (derived from the data fields discharge method & destination). This alternative approach captures mortality for the full patient population, including those that do not have an NHS number (e.g. patients not resident in England) or that for other reasons cannot be linked to Civil Registration data, but it necessarily fails to capture any deaths that occur after the end of the index hospital admission.

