Indicator 6 uses patient-reported outcome measures (PROMs) data that are routinely collected in both NHS and independent hospitals for two surgical procedures: planned hip and knee replacement surgery (see section on datasets above). We will request NHS Digital to supply us with data from the national PROMs programme, which covers NHS-funded care only, linked to a corresponding Hospital Episode Statistics extract.

We will conduct separate multivariate regression analysis of the six indicators stratified by type of procedure. All regression models will include a set of indicator variables denoting the three quadrants, and the associated regression coefficients will be used to test for differences in quality and safety across hospital types and funding sources. All regression models will control for known confounders such as patient demographic characteristics (i.e. sex, age, ethnicity, area-level deprivation based on the index of multiple deprivation score for the patient's lower-layer super output area (LSOA) of residence), diagnosis, comorbidities, past healthcare utilisation as captured in Hospital Episode Statistics, and admission information (e.g. calendar month of admission). In specifying the case-mix adjustment we will draw on previous work [40, 41, 42] and insights from the data quality assessment conducted in WP1.

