It is well known that administrative hospital data do not capture all patient factors that determine outcomes. If unobserved confounders are not equally distributed across admissions in the four quadrants, for example because patients with certain unobserved characteristics are more likely to self-fund their care or be treated in independent hospitals, then this may bias comparative assessments. To explore the impact of unobserved confounding, we will build on our previous work [22, 43, 44] and specify instrumental variable (IV) regression models in which the observed choice of funding source and hospital type (i.e. *selection into treatment* in causal inference terminology) for each admission is modelled as a function of exogenous variation in i) difference in the travel distances to the nearest NHS and independent hospital (as a proxy for ease of access), and ii) median house prices in the patient's LSOA of residence (as a proxy for relative wealth and, thus, affordability of private care). Under the assumptions that these two instrumental variables are not directly correlated with outcome of care (other than through the observed choice of funding source / hospital type) and are strong determinants of the observed choice, this IV approach permits achieving quasi-randomisation in observational data.

Using the result from our analysis we will calculate hospital-level reports for our case-study sites by means of indirect standardisation. For each hospital and indicator, we will calculate the case-mix adjusted outcome (e.g. the rate of unplanned readmissions following planned hip replacement surgery) and plot these using funnel plots; a presentational format of performance assessments that clinicians and managers are increasingly familiar with. We will explore the utility of these data for clinical governance through our case study site fieldwork in WP3.

Qualitative focus groups/interviews with patients and carers to explore quality and safety

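### Indicator 3 counts emergency transfer to an NHS hospital, so its NHS-versus-independent coefficients mix deterioration with escalation route and should not be used to test safety between hospital types

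*Protocol*

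**What the plan says.** All references are to the protocol, WP5, under the heading on quantitative analysis of hospital data. No SAP is at hand.

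- **Definition.** Indicator 3 is "Emergency transfers to NHS hospitals at the end of the index admission episode", scored yes or no. It belongs to a list introduced with "For each index admission we will calculate a set of quality and safety indicators, which have been validated for use with administrative data".
- **Where it is computed.** "Each indicator will be summarised for index admission for quadrants A, B and C". By Diagram 1, A is NHS-funded care in NHS hospitals, B is privately funded care in NHS hospitals, and C is NHS-funded care in independent hospitals.
- **Model and test.** "We will conduct separate multivariate regression analysis of the six indicators stratified by type of procedure". Every model carries the quadrant indicators, and "the associated regression coefficients will be used to test for differences in quality and safety across hospital types and funding sources".
- **Adjustment.** "All regression models will control for known confounders such as patient demographic characteristics". The rest of the list covers diagnosis, comorbidities, past healthcare use and admission details. What a hospital can escalate on site is not named.
- **Unobserved factors.** "To explore the impact of unobserved confounding, we will build on our previous work" introduces instrumental-variable models based on travel distance and local house prices.
- **Hospital reports.** "For each hospital and indicator, we will calculate the case-mix adjusted outcome", followed by funnel plots for the case-study sites.

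Only indicator 4, total length of stay, allows for transfers between hospitals. Indicator 3 is neither limited to one hospital type nor paired with an in-house equivalent, and no caveat on its interpretation is given.

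**The concern.** The outcome is defined by destination. A patient in A or B is already in an NHS hospital. If that patient deteriorates and is escalated within the same hospital, no transfer is recorded. A patient in C with the same deterioration, escalated by a move to the NHS, is recorded as an event. The indicator is therefore a product of two things: how often patients deteriorate, and by which route the hospital escalates. Only the first bears directly on whether care was less safe, yet the coefficient is read as if it measured that alone.

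Research question 3 asks how quality and safety differ between NHS and independent hospitals. A significant C coefficient on this indicator would be reported as part of the answer, and the same measure would go to case-study hospitals in funnel plots. An appropriate transfer would count against the hospital that made it, while an equivalent in-house escalation would leave no trace.

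**Working it through.** The protocol gives no transfer rate, effect size, significance level or sample size for this indicator, so there is no stated figure to reproduce. The direction and form of the bias follow from the definition. The sizes below rest on assumed rates.

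**1. Form of the bias.** Let *d* be the rate of deterioration needing escalation and *t* the share of those cases escalated by transfer to an NHS hospital (for A and B, another NHS hospital).

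- Recorded rate = *d* × *t*.
- Ratio, C to A = (*d*C × *t*C) / (*d*A × *t*A).
- With equal deterioration (*d*C = *d*A), ratio = *t*C / *t*A, whatever the value of *d*.

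**2. Spurious ratio at equal deterioration (all shares assumed).**

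| Share transferred, A | Share transferred, C | Spurious ratio |
|---|---|---|
| 50% | 50% | 1 |
| 25% | 50% | 2 |
| 50% | 100% | 2 |
| 20% | 100% | 5 |
| 10% | 100% | 10 |
| 5% | 50% | 10 |

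Equal shares give no artefact, and a ratio of 10 does not need every case in C to be transferred.

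**3. Chance that the artefact reaches significance.** Assume *d* = 0.5%, *t*C = 100%, 2,000 admissions in C and a two-sided 5% test. Diagram 1 gives A 88% and C 4.6% of elective inpatient care, so A has 2,000 × 88 / 4.6 = 38,261 admissions, taken as 38,000. Expected events in C are 2,000 × 0.005 = 10. With so few events I used Fisher's exact test, summed over the binomial distributions of both counts.

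| Share transferred, A | Expected events, A | Spurious ratio | Chance of a significant difference |
|---|---|---|---|
| 50% | 38,000 × 0.0025 = 95 | 2 | about 49% |
| 20% | 38,000 × 0.001 = 38 | 5 | about 94% |
| 10% | 38,000 × 0.0005 = 19 | 10 | about 99% |
| 100% (equal shares) | 38,000 × 0.005 = 190 | 1 | about 4% |

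An unpooled normal approximation gives 81% for the 10% row, but it is unreliable with 10 expected events. The protocol's sample size summary describes the data as very large. A bigger procedure stratum makes the false signal more likely, because the bias does not shrink with sample size.

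**4. Whether the planned methods remove it.**

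- *Case-mix adjustment* makes patients comparable on *d*. It leaves *t* untouched, because *t* depends on the hospital.
- *Instrumental variables* address selection into funding source and hospital type. Under ideal instruments, or full randomisation, the estimate would be the effect of setting on recorded transfer, which still contains *t*C / *t*A.
- *Indirect standardisation* for the funnel plots inherits the same outcome. If NHS and independent hospitals share one plot, the plot separates them partly by escalation route.

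**5. Which contrasts are affected.** C versus A and C versus B compare different hospital types and are exposed. A and B are both in NHS hospitals, so the mechanism does not bias that contrast in the same way. Comparisons among independent hospitals are also largely free of it, apart from differences in their own facilities.

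**The case against.** **The premise is not in the documents.** The protocol does not describe on-site escalation facilities in either sector. A reader might infer that independent hospitals have to transfer out, that NHS hospitals almost never transfer, and that C is therefore certain to look less safe. The text does not support that. Some independent hospitals may escalate on site, and some NHS patients move to another NHS hospital, so the A and B rates need not be near zero. This stands, and the point must be conditional on a higher transfer share in C.

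**Transfer may itself be a safety matter.** Research question 3 also asks which hospital characteristics are associated with differences, and the background cites an investigation into surgical care in independent hospitals and pathways across the sector interface. Needing an emergency move between hospitals can be a real feature of a setting. This stands in part. It supports reporting the rate as a description of setting. It does not support reading the coefficient as a difference in quality and safety, because in-house escalation is not counted on the NHS side.

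**The indicators are described as validated.** Validation for administrative data supports the coding of the event. It does not show that the event has the same meaning in a hospital that can escalate internally and in one that transfers.

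**Only one of six indicators is affected.** This is correct. No sample size or primary endpoint depends on indicator 3, which limits the severity.

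**Conclusion.** The point holds as a conditional measurement bias. The protocol commits to testing indicator 3 across A, B and C as quality and safety, and its definition records escalation by transfer but not escalation in-house in an NHS hospital. If the transfer share is higher in C than in A and B, the C-versus-A and C-versus-B coefficients and mixed funnel plots are biased against independent hospitals at equal deterioration rates, by a factor equal to the ratio of the shares. That factor is 2 to 10 when C transfers all cases and A transfers 50% to 10%. These shares are assumptions and the true size is unknown.

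A reader might go further and conclude that indicator 3 is unusable in any quadrant comparison, or that any excess in C is false. Neither follows. A versus B is not biased in the same way, and a real difference in deterioration could also be present. The contrast cannot separate the two. Severity: should-fix.

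**What to change.** In the WP5 paragraphs on regression and on hospital-level reports:

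1. State that indicator 3 will not be used to test quality and safety between NHS and independent hospitals.
2. Report it as case-mix adjusted variation within hospital type: among independent hospitals in C, with funnel plots kept separate from those of NHS hospitals. Keep A versus B if the funding-source contrast is wanted.
3. Give any C-versus-A or C-versus-B rate descriptively only, with a statement that it also reflects on-site escalation capability.
4. If the Hospital Episode Statistics extract allows, add a sensitivity analysis with an outcome that counts in-house escalation (such as unplanned critical care) and emergency transfer alike. The protocol's description of the dataset does not mention critical-care fields, so availability must be checked. State that this reduces the asymmetry without fully removing it: escalation to an ordinary ward or a return to theatre within an NHS hospital would still score 0, while a transfer from C for the same reason would score 1.

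The cost is a few sentences of protocol wording and one fewer formal cross-sector test. The other five indicators remain for the NHS-versus-independent comparison.
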